1.1 Objectives and Novelty

We will determine the effects of a whole-fruit-rich diet on glycemic control, liver fat, pancreatic fat, and cardiovascular disease risk factors in weight-stable adults with T2D. Our objectives are three-fold:

- Determine the effects of a diet rich in whole fruit on glycemic control in people with T2D;
- Determine whether T2D remission—or weaning off all diabetes medications and achieving non-diabetic glycemia—is possible without losing weight;
- 3. To determine how eating a diet high in fructose and simple sugars from whole-food sources affects liver fat.

Our clinical trial is novel for three reasons. We will conduct the first rigorously designed clinical trial to support (or refute) current American Diabetes Association (ADA) guidelines that patients with T2D should consume whole fruit. Second, to our knowledge, our study is the first interventional trial to test the effects of eating large doses of whole fruit as a food group. Third, our study is the first dietary trial to test whether patients with T2D can wean off all diabetes medications and achieve non-diabetic glucose levels *without losing any weight*. If this is true, it will be an important milestone achievement.

1.2 Hypotheses

We hypothesize that a whole-fruit-rich diet will improve glycemic control, decrease liver and pancreatic fat, lower blood pressure, and improve serum lipids. We also hypothesize that some participants will wean off their diabetes medications and achieve non-diabetic glycemia during the 12-week intervention. We expect that improvements in glycemic control will be accompanied by restoration of first-phase insulin secretion and reductions in liver and pancreatic fat—similar to studies of VLCDs.

1.3 Primary and Secondary Outcomes

The primary outcome is glycemic control. Glycemic control is difficult to accurately assess whenever antihyperglycemic medications doses change, as changing doses can mask improvements in standard glycemic outcomes. Therefore, we define an individual has having an improvement in glycemic control if s/he needs a lower dose of antihyperglycemic medications (if medication doses change) or has lower mean glucose levels (if medication doses do not change). We will use the following hierarchy of glycemic outcomes:

- 1. Achieving non-diabetic glycemia without antihyperglycemic medications (assessed as a binary outcome and analogous to T2D remission without the 3-month requirement);
- Total dosage of antihyperglycemic medications, as measured by the medication effect score (MES);
- 3. Mean glucose during a three-hour OGTT; and
- 4. Mean 24-hour glucose as measured by continuous glucose monitoring (CGM), adjusted for any changes in medication doses via the MES (see Section 4.5).

We decided to use mean 24-hour glucose as measured by CGM in lieu of HbA1c because CGM more accurately assesses the present glycemic status over the previous week, whereas HbA1c is a lagging indicator of glycemic control. The hierarchy implies that a positive or negative outcome in an upper level will always supersede any findings from lower levels in the hierarchy. In particular, if glucose-lowering medication dosages change, then assessments 1 and

2 will supersede assessments 3 and 4 since changes in glucose-lowering medications confound the interpretation of glycemic data. If there are no changes in glucose-lowering medications, then we will use assessments 3 and 4 to determine whether there are changes in glycemic control. We will interpret the data from assessments 3 and 4 as follows. We will interpret assessment 3 (OGTT) to indicate whether the intervention improves or exacerbates glucose intolerance and underlying defects in glucose metabolism. If there is no change in assessments 1-3, we will interpret assessment 4 (CGM) to reflect only acute changes in the glycemic load and macronutrient composition of the diet. For instance, the intervention may increase mean 24-hour glucose levels in a participant who eats a low-carbohydrate diet at baseline, but this increase may simply reflect switching to a higher carbohydrate diet, not a worsening of glucose metabolism.¹ As another example, the intervention may decrease mean 24-hour glucose levels in a participant who eats a higher glycemic load diet at baseline, but this decrease may reflect switching to a lower glycemic load diet, not an improvement in glucose metabolism per se.

The secondary outcomes are liver fat, pancreatic fat, cardiovascular risk factors, and ancillary measures of glucose metabolism:

- Liver fat, as measured by magnetic resonance imaging and spectroscopy (MRI/S);
- Pancreatic fat, as measured by MRI/S;
- Insulin secretion, as measured by the oral minimal model;
- Insulin sensitivity, as measured by the oral minimal model;
- Mean insulin and C-peptide levels during the OGTT;
- Time-in-range metrics from CGM;
- Mean amplitude of glycemic excursions from CGM;
- HbA1c;

- Fasting glucose;
- Blood pressure;
- Heart rate; and
- Lipids (total cholesterol, LDL cholesterol, HDL cholesterol, and triglycerides).

Additional outcomes include body composition (subcutaneous abdominal fat, visceral fat, and waist circumference), preferences for and sensitivity to sweet tastes, diet satisfaction, food cravings, eating behaviors, mood, quality of life, and depression.

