1.4 Study Design

The trial is a 12-week, single-arm, eucaloric, controlled-feeding trial. During weeks 1–4 (Ramp-Up Phase), adults with insulin-independent T2D progressively eat more fruit, starting at 10% of daily energy and incrementally increasing to 50% while remaining weight-stable. During weeks 5–12 (Main Phase), participants eat 50% of their energy requirements as whole fruit (~16.4 servings/day) and the remaining 50% as a Mediterranean-style diet. By design, the aggregate diet is a high-carbohydrate diet, rich in simple carbohydrates in whole-food form. Food is prepared for participants in a metabolic kitchen, and participants must eat the provided study food. At week 10, participants who achieve non-diabetic levels of glycemia—defined as mean 24-hour glucose <140 mg/dl (equivalent to HbA1c <6.5% or <)—are taken off their antihyperglycemic medications to see if they can maintain non-diabetic glycemia without the use of medication. All study outcomes are measured at week 0 (baseline), week 4 (end of Ramp-Up Phase), and week 12 (end of Main Phase).

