3.2 Cessation of Glucose-Lowering Medications

At the end of week 10, we will cease all antihyperglycemic medications in participants who achieve a mean 24-hour glucose of <140 mg/dl for at least one week during weeks 8–10. Participants whose baseline 24-hour glucose values are <140 mg/dl must additionally experience a 10% reduction in mean 24-hour glucose to ensure they have genuinely experienced a clinically meaningful improvement. Prior to week 10, participants' medications will not be adjusted unless there are safety concerns or associated adverse events.

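### Drugs are stopped by rule at week 10, so the week-12 MES drop in those participants does not show a lower need, and Section 1.3 does not settle whether it counts as improvement

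*Combined protocol and SAP*

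**What the plan says.** Section 1.3 defines individual improvement in two branches. If doses change, "we define an individual has having an improvement in glycemic control if s/he needs a lower dose of antihyperglycemic medications (if medication doses change"); glucose decides only if doses stay the same. The primary outcome is then a four-level hierarchy: level 1 is non-diabetic glycemia off drug, level 2 is "Total dosage of antihyperglycemic medications, as measured by the medication effect score (MES"), level 3 is OGTT mean glucose, and level 4 is mean 24-hour CGM glucose adjusted for MES (formula in Section 3.5). The general rule is that "a positive or negative outcome in an upper level will always supersede any findings from lower levels in the hierarchy". When doses change, assessments 1 and "2 will supersede assessments 3 and 4 since changes in glucose-lowering medications confound the interpretation of glycemic data". For the other case the section says: "If there are no changes in glucose-lowering medications, then we will use assessments 3 and 4".

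The dose change itself is a protocol action. At the end of week 10 the team will "cease all antihyperglycemic medications in participants who achieve a mean 24-hour glucose of <140 mg/dl for at least one week" during weeks 8–10. Those already below 140 mg/dl at baseline "must additionally experience a 10% reduction in mean 24-hour glucose" (Section 3.2). Section 1.4 gives the reason: participants who qualify "are taken off their antihyperglycemic medications to see if they can maintain non-diabetic glycemia without the use of medication". Before then, doses are held except for safety.

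Section 4.4 makes weeks 0 versus 12 the primary comparison, analyses continuous outcomes with random-intercept models, and reports the percentages improved, unchanged and worse in glycemic control.

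**The concern.** The stop opens the maintenance test; it is not the result of that test. A participant whose drugs are withdrawn has an MES of 0 at week 12 because one on-drug week was below the threshold, whether or not glucose stays there once the drugs are gone. Level 1 records a rebound correctly. Level 2 still records a full drop in MES, and nothing in the plan says how that drop is scored when level 1 fails. Section 1.9 names values above 300 mg/dl as grounds for considering a medication change, so a moderate rebound would not by that number restore the MES.

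Two results are at stake: the percentage of participants classed as improved on the primary outcome, and the interpretation of the week 0 to 12 MES test. A smaller matter is that time-in-range and MAGE, both listed secondary outcomes, compare on-drug week 0 with off-drug week 12 in these participants, and Section 3.5 adjusts only mean glucose for MES.

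**Working it through.** **The plan's own figure.** Section 4.3 states 81% power for level 1 (18.0% against 0.7%, 16 completers). Under 0.7%, P(X≥1) = 0.106 and P(X≥2) = 0.0055, so two cases are needed. Under 18%, P(X≥2) = 1 − 0.82^16 − 16 × 0.18 × 0.82^15 = 0.811. This reproduces and is not in dispute. The plan gives no corresponding figure for MES.

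**Step 1: the two readings on one case.** Formula (Section 3.5): adjusted glucose = mean + 28.7 × MES. Assumed: baseline 145 mg/dl on MES 1.0, so adjusted 145 + 28.7 = 173.7; one on-drug week at 138, so drugs are stopped.

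| Week-12 mean, off drug | Level 1 | MES change | Adjusted change | Improved if MES decides | Improved if level 1 decides |
|---|---|---|---|---|---|
| 166.7 | not met | −1.0 | −7.0 | yes | no |
| 180 | not met | −1.0 | +6.3 | yes | no |

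The MES drop and the adjusted value point in opposite directions only if the week-12 mean exceeds 145 + 28.7 × MES, which is 159.4, 173.7 or 188.1 mg/dl for MES 0.5, 1.0 or 1.5.

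**Step 2: the MES test.** Assumed: n = 16; k participants have equal MES drops to 0 between weeks 4 and 12; no other dose changes. The size of the common drop cancels, so 1 is used.

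- Paired t-test (15 df): t² = k(n−1)/(n−k). For k=3, 45/13 = 3.46, t = 1.86, p=0.083. For k=4, 60/12 = 5, t = 2.24, p=0.041.
- Random intercept, time categorical (weeks 0, 4, 12; 30 df): residual sum of squares = (2/3)k(1−k/n). For k=3 this is 1.625, so the mean square is 0.0542. The difference is −3/16 = −0.1875, SE = √(2 × 0.0542/16) = 0.0823, t = −2.28, p=0.030. For k=2, p=0.083.
- Random intercept, time linear (31 df): the sum of squares of time is 74.67 per participant, 1,194.67 in all. For k=3 the slope is −20/1,194.67 = −0.01674, the residual sum of squares is 2 − 0.335 = 1.665, SE = √(0.0537/1,194.67) = 0.00671, t = −2.50, p=0.018. For k=2, p=0.057.

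The mixed model needs fewer stops because the absence of change between weeks 0 and 4 lowers its residual variance. With unequal drops (MES uniform on 0.5–2.0), three stops give p<0.05 in 93% of draws (categorical) and over 99.9% (linear). The paired test does so in 42% of draws at four stops and 99.9% at five.

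**Step 3: stops by chance alone.** Assumed: no diet effect; weekly means normal around a true on-drug mean μ. With independent weeks and p = Φ((140−μ)/SD), the probability is about (1−p)[1−(1−p)³], ignoring the rare cases that start below 140. For μ=145, SD 5: p = 0.159, and 0.841 × (1 − 0.841³) = 0.340. Simulation with the full criterion gives:

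| True on-drug mean | SD 5, corr. 0 | SD 5, corr. 0.5 | SD 8, corr. 0 | SD 8, corr. 0.5 |
|---|---|---|---|---|
| 145 | 0.340 | 0.214 | 0.446 | 0.282 |
| 150 | 0.065 | 0.049 | 0.255 | 0.166 |
| 155 | 0.004 | 0.004 | 0.086 | 0.063 |
| 160 | 0.0001 | 0.0001 | 0.019 | 0.015 |

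The SD matters. At zero correlation, SD 10 and 15 give about 0.47 and 0.52 at 145, and 0.065 and 0.23 at 160.

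**The case against.** The strongest reply is that the text already contains the answer. Section 1.3 speaks of the dose a participant needs, not the dose taken, and a negative result at an upper level overrides lower ones. Maintenance off drug is tested only in people taken off drug. For them doses changed, levels 1 and 2 govern, and level 1 outranks level 2, so a rebound is a negative level 1 result that cancels the MES drop. Participants with unchanged doses still go to levels 3 and 4. This reading is coherent, and a reader who infers that the plan definitely scores a rebound as improvement goes further than the text. What stands is that the plan does not state this reading. Need is measured only as total dosage. Taken without the restriction to stopped participants, the override rule would leave levels 2 to 4 unused for everyone who fails level 1, which conflicts with the use of levels 3 and 4 when doses are unchanged.

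A second reply is scale. A reader might infer that the percentage improved will be inflated by 25 points (4/16). That presupposes four stops without any diet effect. At the Step 3 rates, four expected chance stops need 4/0.446 = 9 to 4/0.214 = 19 drug-treated completers at a true mean of 145, and 16 to 82 at 150. Drug use is not an entry criterion. On the plan's equivalence of 140 mg/dl with HbA1c 6.5% and its slope of 28.7, the eligible 6.0–9.5% spans about 126 to 226 mg/dl, so 145–150 is a narrow part of it. The documents do not support a fixed inflation figure.

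Third, the stop is not arbitrary: it requires on-drug glucose below 140 mg/dl, with a further 10% fall if baseline was already below. A rebound would also remain visible at levels 1 and 4. Both points are correct, and they limit the damage. They do not make the level 2 test interpretable alone.

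Finally, the week 0–4 comparison and the CGM trajectory analysis give some pre-cessation information on CGM outcomes, though not a planned contrast up to the end of week 10.

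**Conclusion.** The concern holds as an ambiguity with consequences, not as a settled scoring error. Two defensible readings of Section 1.3 classify the same rebounding participant differently on the primary outcome, so Sections 1.3, 1.4, 3.2 and 4.4 must be reconciled.

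Under either reading, three stops (random-intercept model) or four (paired t-test) among 16 completers can make the MES change significant regardless of later glucose. This rests on equal drops, no restarts and no other dose changes; the paired result at four stops is sensitive to unequal drops. The number of stops is unknown. Stops by chance alone are common only when the true on-drug mean is near or not far above 140 mg/dl: 21–45% at 145 and at most 2% at 160, for an assumed weekly SD of 5–8 and correlation 0–0.5.

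A reader might also infer that the level 1 test or MES-adjusted glucose is compromised, or that unadjusted mean glucose is. The first two are not affected by this problem, and unadjusted mean 24-hour glucose is not a listed outcome. For time-in-range, withdrawal would be expected to bias week 12 against the diet, so it would not be expected to create a false benefit.

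**What to change.** The cessation rule does not change.

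1. In Sections 1.3 and 4.4, state that for participants stopped under Section 3.2 the MES drop alone is not an improvement. Level 1 at week 12 decides whether the lower dose counts as needed, and a participant who fails level 1 after cessation is not classed as improved on MES. Say which remaining category that participant enters, and that levels 3 and 4 still apply when doses are unchanged. Show MES-adjusted mean glucose alongside for those stopped. Using the adjusted value as the deciding rule would be less suitable: it would place level 4 above level 2, and in the no-effect simulation (means 145–150, SD 5–8) it would still class 51–66% of stopped participants as improved.
2. Report the MES test together with the number of protocol-driven stops, and not as stand-alone evidence of benefit.
3. For time-in-range and MAGE, add a contrast of baseline with the last full valid CGM week up to the end of week 10, using the same window for all participants. Label week 12 as post-cessation and note the expected direction of bias for time-in-range.

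The cost is SAP wording and some re-tabulation, since CGM is already worn every week (Section 3.5, Table S2). The downside is that fewer participants may be classed as improved, and the added contrast covers about 10 weeks of diet, not 12.

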4.3 Power Calculation

As this is a pilot and feasibility trial, the sample size was not based on a power calculation. We selected a sample size of 16 completers to provide sufficient data to inform the design of a future trial. Nonetheless, our study has 81% power to detect an 18.0% rate of attaining non-diabetic glycemia vs. a spontaneous remission rate of 0.7%.²³ Further, 16 completers provides 80% power to detect effect sizes of Cohen's d ≥ 0.78 , using a two-tailed paired t-test with α =0.05. This corresponds to a large effect size, which we expect, as participants eat a very large amount of fruit. We acknowledge that we are not powered to detect medium or small effect sizes, which may also be clinically relevant.

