4.4 Statistical Analyses

All statistical tests will be two-sided with a Type I error rate of α =0.05. Because this is a controlled-feeding trial—designed to determine the cardiometabolic effects under conditions of nearly perfect adherence—we will analyze the data per protocol in completers only. The primary comparison will be between weeks 0 and 12, with secondary comparisons between weeks 0 and 4 and between weeks 4 and 12. Data may be Winsorized if there are outliers with an overwhelming degree of influence or values that are non-physiologic . We will test whether a fruit-rich diet can induce non-diabetic glycemia without hyperglycemia medications by testing whether our observed "remission" rate differs from the spontaneous T2D remission rate of

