Appendix

Table S1. Eligibility Criteria.

Inclusion Criteria

- Aged 20–70 years
- BMI \leq 45.0 kg/m²
- First diagnosed with T2D within the past six years
- HbA1c between 6.0–9.5%

Exclusion Criteria

- On insulin
- Diagnosis of diabetes before age 18
- eGFR <45 ml/min per 1.732 m²
- Heart attack in the past six months or severe or unstable heart failure
- Significant gastrointestinal disease, major gastrointestinal surgery, or gallstones
- Significant cardiovascular, renal, cardiac, liver, lung, adrenal, or nervous system disease that might compromise the participant's safety or data validity
- Evidence of cancer (other than non-melanoma skin cancer) within the last five years
- Clinically significant laboratory abnormality
- Change in the dosage of a chronic medication that may affect study endpoints within the past three months
- On weight loss medication
- Lost or gained >5 kg of weight in the past six months
- Pregnant, planning to become pregnant in the next 12 months, or breastfeeding
- Major psychiatric condition that would affect the ability to participate in the study
- Not able to eat the provided study meals (e.g., food allergies)
- Behavioral factors or circumstances that may impede adhering to the dietary intervention
- Not able to do the abdominal MRI scan (e.g., claustrophobia, implanted metal objects, body diameter >60 cm)
- Not willing to wear a mask and/or comply with other COVID-19 precautions

Figure S1. Study Menu. Shown below is the 7-day menu during the main phase of the study

(weeks 5-12).

Sunday	Monday	Tuesday	Wednesday	Thursday	Friday	Saturday						
Breakfast												
Mixed Berry	Raspberry	Peach Smoothie	Strawberry	Cherry	Mango	Blueberry						
Smoothie	Smoothie	reach Shioothic	Smoothie	Smoothie	Smoothie	Smoothie						
Lunch												
Tomato-Garlic	Corn,	Farro and	Chickpeas and	Sweet Potato	Oatmeal	Vegetable and						
Lentil Bowl	,,, _,, _		Broccoli with	and Kidney		Hummus						
	Sweet Pepper	Vegetables with	Pesto Parmesan	Bean Bowl	Soy Milk	Sandwich on						
Walnuts	ts Salad Mozzar					Ezekiel Bread						
			Dried Figs	Pumpkin Seeds	Pecans							
Dried Mango	Brazil Nuts	Almonds			_							
	D 1 1 D 1			Dried	Dates	Almonds						
	Dried Peaches	Dried Apricots		Pineapple		D' 1E'						
						Dried Figs						
	1	2	Snack (Fruit Sala	d)	I	1						
Clementines,	Strawberries,	Blueberries,	Cantaloupe,	Clementines,	Strawberries,	Cantaloupe,						

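### The rate of off-drug non-diabetic glycemia is tested against a T2D remission rate with a different definition, so rejecting that null does not by itself show that the diet caused it

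*Combined protocol and SAP*

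**What the plan says.** **Design.** "The trial is a 12-week, single-arm, eucaloric, controlled-feeding trial" (Section 1.4). There is no concurrent control, so an external rate has to serve as the comparator.

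**Endpoint.** Level 1 of the primary hierarchy in Section 1.3 is drug-free non-diabetic glycemia, "analogous to T2D remission without the 3-month requirement". Section 3.1 sets the criterion as a 24-hour mean glucose under 140 mg/dl over the past week. Under Section 3.2, drugs stop at the end of week 10 for those who qualified in weeks 8–10. Outcomes are read at week 12, so these participants are about two weeks off drugs.

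**Remission, for comparison.** Section 3.1 gives the consensus definition as HbA1c below 6.5%, or in some cases a two-week mean glucose under 140 mg/dl, at least three months after all drugs are stopped.

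**Test.** Section 4.4 asks whether the diet can induce the outcome by testing, with an exact binomial test, whether the observed "rate differs from the spontaneous T2D remission rate". It prints the null as 0.07%. Section 4.3 bases its power statement on "a spontaneous remission rate of 0.7" percent. "All statistical tests will be two-sided with a Type I error rate of α =0.05" (Section 4.4). If at least one case occurs, Section 4.4 adds a bootstrap 95% interval.

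**Entry.** Table S1 admits "HbA1c between 6.0–9.5" percent. Section 3.2 has a rule for "Participants whose baseline 24-hour glucose values are <140 mg/dl": they must also show a 10% fall before drugs are stopped.

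**The concern.** A one-sample test is only as good as its null. Here the null is the rate of one outcome and the observed proportion is the rate of another. The trial's endpoint needs about two weeks off drugs where remission needs three months, and one week of glucose data where the CGM form of the remission definition uses two.

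Two features make a higher background plausible. Entry is open to people with an HbA1c of 6.0% to 6.4%, below the 6.5% mark that Section 3.1 equates with 140 mg/dl, and no listed criterion requires drug treatment at entry. The 10% fall that guards against counting people who start below the threshold is written as a condition for stopping drugs and is not repeated in the Section 3.1 endpoint definition.

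This level supersedes every other level of the primary hierarchy. With 16 completers, one or two participants would be enough to reject. If the background for this endpoint is well above the null, a nominal 5% test can support the claim that the diet induces non-diabetic glycemia when it does not.

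**Working it through.** **Inputs.** n = 16 ("We selected a sample size of 16 completers", Section 4.3); null p0 = 0.7% (Section 4.3) or 0.07% (Section 4.4); alternative 18.0% (Section 4.3); two-sided α = 0.05 (Section 4.4). The documents give no background rate for the trial's endpoint, so the rates in step 2 other than 0.7% are assumptions.

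**1. Reproduce the stated power.**

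P(X≥1) = 1 − (1−p)^16, and P(X≥2) = 1 − (1−p)^16 − 16p(1−p)^15.

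- At p = 0.007: P(X≥1) = 1 − 0.8937 = 0.106, which is too large. P(X≥2) = 1 − 0.8937 − 0.1008 = 0.0055. The test therefore rejects at 2 or more of 16.
- At p = 0.18: P(X≥2) = 1 − 0.0418 − 0.1468 = 0.811. This is the stated 81%.
- At p = 0.0007: P(X≥1) = 1 − 0.9889 = 0.011, so one success rejects. Power at 18% would be 1 − 0.82^16 = 0.958, not 81%.

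The power figure therefore belongs to 0.7%. The choice of null moves the critical count from 2 to 1.

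**2. Chance of rejecting with no diet effect**, if the true background for this endpoint is p:

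| Background p | Rule ≥2 of 16 (0.7% null) | Rule ≥1 of 16 (0.07% null) |
|---|---|---|
| 0.7% | 0.6% | 10.6% |
| 2% | 4.0% | 27.6% |
| 3% | 8.2% | 38.6% |
| 5% | 18.9% | 56.0% |
| 10% | 48.5% | 81.5% |

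**3. Largest background at which size stays at or below 5%.**

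- Rule ≥1: 1 − 0.95^(1/16) = 0.32%.
- Rule ≥2: solving P(X≥2) = 0.05 gives 2.27%, or 16 × 0.0227 = 0.36 expected participants.

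**4. What an interval would say.** The Clopper-Pearson lower limit solves P(X≥x) = 0.025: 2/16 gives 1.6%, 3/16 gives 4.0%, 4/16 gives 7.3%. At 0/16 the interval runs from 0 to 1 − 0.025^(1/16) = 20.6%.

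The SAP does not name the type of bootstrap. For a percentile bootstrap, the lower limit is 0 whenever (1 − x/16)^16 exceeds 0.025. The values are 0.356, 0.118 and 0.036 for x = 1, 2, 3, and 0.010 for x = 4. So for 1 to 3 successes that lower limit is 0 and excludes no background rate. At 0/16 no interval is planned.

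**The case against.** **The direction of the bias is not proven.** A reader might infer that the background for the looser endpoint must be at least as high as the cited rate. That follows only if the cited rate uses the same glucose criteria and a comparable time window. The documents give neither for reference 23. If that rate covers longer than 12 weeks, the 12-week background could be lower. The trial also holds weight stable, and nothing shows that the cited population did. This objection stands: a higher background is plausible, not established.

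**The error need not be large.** A reader might infer that false claims would be frequent. At an assumed 2% background the ≥2 rule rejects 4.0% of the time, still under 5%, and it holds its size to more than three times the 0.7% null. The 18.9% and 48.5% figures need backgrounds of 5% and 10%, for which the documents offer no evidence. This also stands, but only for the 0.7% null; under the 0.07% printed in Section 4.4 the margin is much thinner.

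**The endpoint has more than one hurdle.** Those stopped at week 10 must first qualify in weeks 8–10 and then stay under 140 mg/dl off drugs, and those with low baseline glucose need the 10% fall to have drugs stopped. These steps make chance success harder. They do not turn the endpoint into remission, and the 10% rule is not written into the endpoint.

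**The plan is candid.** It discloses the missing three months, calls the endpoint a proxy, calls the trial a pilot and plans an interval. All true, but the null is left unadjusted and the test is still assigned the causal question.

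**Any single-arm trial has this limit.** Correct: even a matched historical null would not replace a control group. The mismatch of definitions is an additional problem.

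**Conclusion.** The concern holds as a limit on what the test can conclude. The endpoint and the null differ by the protocol's own account, and no matched background rate is given. Rejection would show that the observed rate exceeds the cited remission rate; it would not by itself show that the diet induced non-diabetic glycemia.

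The documents do not support the stronger reading that the type I error is known to be inflated. Its size depends on an unknown background: the ≥2 rule is safe up to about 2.3%, the ≥1 rule only up to about 0.32%. The power arithmetic in Section 4.3 is sound for 0.7%. The disagreement between 0.7% and 0.07% is a separate inconsistency that changes the critical count and has to be settled in any case.

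**What to change.** 1. Reconcile the null rate in Sections 4.3 and 4.4, and state the remission definition and follow-up window behind the cited figure.
2. In Section 4.4, make the level 1 count with its Clopper-Pearson 95% interval the main result, including at 0 of 16, in place of the bootstrap interval.
3. State the lower limit as the largest background rate that the data exclude (2/16: 1.6%; 3/16: 4.0%; 4/16: 7.3%).
4. Label the comparison with the spontaneous remission rate as descriptive, because the endpoint omits the three-month requirement.
5. Give exact p-values at 0.7%, 2%, 5% and 10% as a sensitivity range. Note that the interval puts 2.5% in each tail and can differ slightly from them: 2/16 gives p = 0.040 against 2%, although its lower limit is 1.6%.

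**Cost.** SAP wording and a four-line table, with no change to conduct, sample size or clinical management. The downside is a weaker headline claim. Against a 5% null, for example, the critical count would be 3 and power at 18% would be 57%; against 10%, the count would be 5 and power 15%.
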